### **2.2 Secondary Objectives**

- To describe the efficacy of intra-anal imiquimod 2.5% for treatment of anal HSIL compared to observation only. Note: this objective is no longer powered to establish efficacy.
- To assess the safety and tolerability of intra-anal imiquimod 2.5% and topical 5FU.
- To compare the efficacy of intra-anal imiquimod 2.5% and topical 5FU.
- To assess for partial response of intra-anal imiquimod 2.5% or topical 5FU as compared to observation only.
- To evaluate the effect of intra-anal imiquimod 2.5% and topical 5-FU on HPV persistence.
- To evaluate anal HSIL outcomes at Week 44.
- To evaluate the effect of behavioral patterns including tobacco smoking and sexual activity on treatment efficacy, tolerability, and HPV.

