#### 6.4 Visit 3 (Week 8) +/- 14 days

6.4.1 The following evaluations will be performed, and laboratory samples will be collected for all participants:

- Clinical assessment: The participant's medical history will be updated for any changes. A review of systems for any new or changed local symptoms, such as hematochezia, dyschezia, erythema, swelling, or pruritus. A targeted physical exam should be performed as indicated (see [Section 6.2.1](#)).
- Pregnancy test: Urine or serum beta-HCG will be performed (and results obtained) when indicated (women of childbearing potential).
- Anal swab for HPV testing.
- For study participants randomized to the 5-fluorouracil 5% arm only: HRA will be performed provided that the participant is not experiencing significant anal discomfort from the study treatment. In such a case, anoscopy should be performed without soaking the anal canal with acetic acid. Acetic acid and/or Lugol's solution should only be used sparingly to avoid further participant discomfort. The number of involved octants, location, and percent circumference of HSIL will be documented. Anal biopsies should be performed only if the clinician notes suspicious friability, ulceration, mass effect, heaped-up borders, and/or markedly abnormal vascular pattern. This could be indicative of progression of the lesion toward invasive disease.
- HRA may be performed in the observation arm if disease progression is suspected.
- If performing HRA, all lesions, all aspects of the anal transformation zone, distal canal and perianus will be photographically documented.
- Collect study diary and evaluate treatment adherence. Additional instruction on proper administration of study treatment should be given as needed. Partially used containers should be weighed to measure the amount of cream used. Participants will receive new replacement containers as needed for their

appropriate study arm. Study agent must be weighed prior to distribution to the participant to allow for accurate measurement of adherence.

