## 10.8 Secondary Analyses

To examine the tolerability and safety of the three arms, descriptive statistics for AEs will be computed. AEs will be summarized at the event level and subject level according to severity. AEs will be stratified according to those reported at or before Week 20 and after Week 20 since those in the observation arm have to option of being randomized to imiquimod or 5FU at Week 20. Proportions and their exact binomial 95% confidence intervals will be calculated. We will compute summary statistics for the amount of study drug taken by measuring the mass of study drug dispensed (weight of study drug container at baseline – weight of study drug at the end of treatment).

Similarly, we will assess for PR in two ways. We will compare between arms the number of quadrants with HSIL found on biopsies treating the response as an ordinal variable. The biopsy plan for Week 20 and 48 (see [Appendix V](#)) specifies that at least one biopsy be obtained from each quadrant. Biopsies used for eligibility will generally be obtained through routine care and will not necessarily have four quadrant biopsies, so we are not able to look at the within participant change in the number of quadrants with HSIL on biopsy. Therefore, this comparison between arms assumes that the extent of disease at enrollment is balanced between arms, which is reasonable given randomization. We will also compare the proportion of participants achieving CR or PR (as per [Section 9](#)) with imiquimod or 5FU as compared to observation only using similar approaches as the primary objective.

We will evaluate the effect of imiquimod and 5FU on persistence of HPV type specific infections. We will report the frequency and proportion of HPV types present at baseline that are no longer detected at Week 20. We will also report the frequency and proportion of new HPV infections detected at Week 20 that were not present at baseline. Proportions and their exact binomial 95% confidence intervals will be calculated.

HSIL outcomes at Week 44 will be analyzed similarly to those at Week 20. Results for the observation arm will be stratified into cross-over treatment groups.

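### The HPV paragraph of 10.8 aims at a treatment effect on persistence but names no 5FU-minus-observation estimate, and its exact binomial intervals, if taken over HPV types, ignore clustering within participants

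*Combined protocol and SAP*

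**What the plan says.** Section 2.2 lists this secondary objective: "To evaluate the effect of intra-anal imiquimod 2.5% and topical 5-FU on HPV persistence". Section 10.8 restates it as "We will evaluate the effect of imiquimod and 5FU on persistence of HPV type specific infections".

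The analysis that follows in the same paragraph has three parts:
- Loss of baseline types: "We will report the frequency and proportion of HPV types present at baseline that are no longer detected at Week 20"
- Acquisition: types that appear at Week 20 but were absent at the start are counted and given as a share.
- Inference for both summaries: "Proportions and their exact binomial 95% confidence intervals will be calculated"

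The paragraph does not define persistence, does not say whether the proportions are shown by arm, and names no contrast with observation. For partial response, the same section does name one: "We will compare between arms the number of quadrants with HSIL found on biopsies treating the response as an ordinal variable".

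The swabs exist in both arms. At Week 8, Section 6.4 states that "The following evaluations will be performed, and laboratory samples will be collected for all participants", and its list includes "Anal swab for HPV testing". Section 6.5 schedules the Week 16 swab with no restriction by arm. Section 6.6.1 schedules the Week 20 swab for everyone. Appendix II agrees.

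The last paragraph of 10.8 plans regression models for the link between smoking, sexual behavior and several endpoints, HPV among them. It permits GEE for endpoints measured over time, and it commits to a model that includes treatment arm alongside the behavioral covariates.

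**The concern.** An effect on persistence is a comparison. Some HPV types will clear in untreated people, and some persisting types will be missed on a given swab. Both add to the share no longer detected at Week 20, whatever 5FU does. An interval around one arm's share describes that mixture and does not estimate the effect that the objective asks for. The randomised observation arm supplies the missing reference, but the paragraph does not use it in a stated estimate.

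The second problem is the unit. As worded, the proportion is of HPV types. A participant may carry several, and their fates are likely to be correlated through shared adherence, immune status and swab quality. An exact binomial interval treats every type as an independent observation and is too narrow when they are positively correlated.

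At stake is whether this secondary objective gets an interpretable answer. The primary endpoint is not affected.

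**Working it through.** The documents give no HPV clearance rate, assay sensitivity or power for this objective, so there is no stated figure to reproduce. The first check is textual; the rest is illustration on assumed values.

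**1. Text side by side.** Sections 2.2 and 10.8 ask for an effect. The HPV paragraph of 10.8 supplies two Week 20 proportions with one-sample intervals. The partial-response paragraph supplies a between-arm comparison. The closing model of 10.8 includes treatment arm and HPV, but it does not say which HPV outcome (any HPV, type-specific, clearance, new infection), which time points or which effect measure.

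**2. What a single-arm share shows when 5FU does nothing.** Let c be natural clearance by Week 20 and s the chance that a persisting type is detected on one swab. Assumed ranges: c = 10-40%, s = 80-95%.

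Apparent clearance = c + (1 − c)(1 − s)
- c = 0.10, s = 0.95: 0.10 + 0.90 × 0.05 = 14.5%
- c = 0.20, s = 0.90: 0.20 + 0.80 × 0.10 = 28%
- c = 0.40, s = 0.80: 0.40 + 0.60 × 0.20 = 52%

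In the middle case, 29 of 105 types has an exact 95% interval of 19.3% to 37.2%. That interval is well clear of zero although the drug effect is nil. With equal detection in both arms, observation also shows 28% and the difference is zero. Only the contrast reveals this.

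**3. Clustering of types.** Section 10.1 gives 35 participants per arm. Assume k baseline types each and intraclass correlation ρ.

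Design effect = 1 + (k − 1)ρ; effective number = 35k / design effect
- k = 3, ρ = 0.3: 1 + 2 × 0.3 = 1.6; 105 / 1.6 = about 66
- Range over k = 2-4 and ρ = 0.1-0.5: design effect 1.1 to 2.5

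Interval width scales with the square root: √1.6 = 1.26, so the half-width of about 9 points in step 2 becomes about 11. Over the range, intervals should be about 5% (√1.1) to 58% (√2.5) wider.

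**4. Precision of a contrast.** With one binary result per participant, 35 per arm, two-sided 0.05 and 28% on observation, power is about 41% for +20 points, 73% for +30 and 85% for +35. A participant-level proportion could be somewhat more precise. This supports an estimate with an interval, not a powered test.

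**5. Would two negative swabs be a better definition?** Assume true clearance of 50% on 5FU and 20% on observation, with independent misses.
- One swab (Week 20): s = 0.8 gives 60% vs 36% (24 points); s = 0.9 gives 55% vs 28% (27 points).
- Weeks 16 and 20 both negative, all clearance complete by Week 16, c + (1 − c)(1 − s)²: s = 0.8 gives 52% vs 23.2% (28.8 points); s = 0.9 gives 50.5% vs 20.8% (29.7 points).
- Same rule, but 20% of clearances in each arm fall between Weeks 16 and 20, 0.8c + 0.2c(1 − s) + (1 − c)(1 − s)²: s = 0.8 gives 0.40 + 0.02 + 0.02 = 44% vs 0.16 + 0.008 + 0.032 = 20% (24 points); s = 0.9 gives 41.5% vs 17.2% (24.3 points).

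The gain from two swabs disappears under modest late clearance.

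**The case against.** The strongest reply is that 10.8 does plan a treatment-arm analysis of HPV. Its last paragraph commits to a model with treatment arm for endpoints that include HPV, and it allows GEE, which could use the Week 8 and Week 16 swabs. A reader might therefore infer too much from the HPV paragraph alone, namely that no HPV comparison with observation is planned and that the interim swabs are ignored. The documents do not support either reading for 10.8 as a whole. What the model leaves open is the estimate at issue here: it serves the behavioral objective, its HPV outcome and effect measure are unspecified, and GEE is optional.

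A reader might also infer that the plan credits natural clearance to 5FU. It does not say so. The proportions may be shown by arm, in which case the observation column displays background clearance and missed detections. With equal detection in both arms, missed detections raise both arms alike when there is no effect and shrink a real difference. They do not create one.

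Finally, a reader might conclude that clearance must be redefined as two consecutive negatives. The documents point the other way. Topical treatment may start up to two weeks after randomization (6.2.1), the Week 16 visit has a 14-day window either side (6.5), and the last dose may come as late as Week 19 (5.3.1). Week 16 swabs may therefore be taken during dosing. Week 20 must follow the last dose by at least two weeks (6.6). Single-visit Week 20 detection is a defensible choice, and step 5 shows that two swabs need not do better.

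**Conclusion.** The point holds for the HPV paragraph of 10.8. It states a treatment effect as its aim, plans only Week 20 proportions, and names no 5FU-versus-observation estimate. The closing model of 10.8 does not fill that gap. If the unit is the HPV type, as the wording reads, the exact binomial intervals also ignore correlation within participants.

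The size can only be illustrated. On the assumed ranges, 14.5-52% of baseline types would appear cleared with no drug effect, and intervals over types should be roughly 5-58% wider. These figures rest on assumed clearance, detection, types per person and intraclass correlation, none of which is in the documents.

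Two stronger conclusions do not follow: that Week 20 is the wrong time point, and that single-swab misses seriously distort the comparison. On the assumptions of step 5 those misses shrink a 30-point difference by 3-6 points. With 35 per arm and one binary result each, the 95% half-width at 55% vs 28% is 1.96 × √[(0.55 × 0.45 + 0.28 × 0.72) / 35] = about 22 points.

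The change should be made, but it concerns a secondary objective only.

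**What to change.** In the HPV paragraph of 10.8:
- Make the main result the difference, 5FU minus observation, in each participant's proportion of baseline HPV types no longer detected at Week 20. Compute the 95% interval at participant level or with a cluster-robust method. State that participants with no type at baseline do not enter this measure.
- Do the same for types newly detected at Week 20, with the denominator stated.
- Label both as estimates, not powered tests, at 35 per arm.
- Keep Week 20 as the main time point because of its guaranteed interval after the last dose. Show Week 8 and Week 16 detection by arm, and use negatives at both Week 16 and Week 20 as a sensitivity analysis only.
- Say how this estimate relates to the treatment-arm model in the last paragraph of 10.8.

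The cost is a few sentences and modest extra programming. All the swabs are already scheduled in both arms, and no procedure changes.

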## **10.9 AMC Policy for Monitoring of Phase III Trials**

10.9.1 This study will be monitored by the AMC DSMB, as outlined in its Charter and as required by the NCI Data and Safety Monitoring Policy for Phase III investigations. The study will adhere to the AMC Data Safety Monitoring Plan ([Appendix VIII](#)).

10.9.2 Central Pathology Review

Slides from all biopsies used for eligibility and slides from all biopsies obtained post-randomization will be submitted for central review by a single pathologist. Any discrepancies of interpretation (normal, low-grade AIN, or high-grade AIN) will be referred for adjudication.

## **10.10 Publication of Research Findings**

Publication of the results of this trial will be governed by AMC policies.

## **11.0 ETHICAL AND REGULATORY CONSIDERATIONS**

### **11.1 IRB Approval and Informed Consent**

The principles of Institutional Review Board (IRB) approval and informed consent described in the Food and Drug Administration (FDA) regulations (21 CFR Part 50 and 56) and Department of Health and Human Services (DHHS) regulations for the Protection of Human Subjects regulations (45 CFR Part 46) must be followed. IRB approval of the protocol and the informed consent form must be given in writing.

The sponsor's designee (AMC ODMC) must receive a copy of the letter of approval from the IRB, which specifically approves the protocol and informed consent, before subject enrollment. The IRB must also approve any significant changes to the protocol and documentation of this approval must be sent to the AMC ODMC. The IRB must review the research project at least once every 365 days during the duration of the project. Continuing approval of the project must also be given in writing and provided to the AMC ODMC.

Records of all study review and approval documents must be kept on file by the Investigator and are subject to inspection during or after completion of the study. AEs must be reported to the IRB according to local procedures. The IRB should receive notification of completion of the study and final report within 3 months of study completion and termination. The Investigator will maintain an accurate and complete record of all submissions made to the IRB, including a list of all reports and documents submitted.

Written informed consent will be obtained from the subject. The nature, significance, and risks associated with the study must be explained to the subject. The informed consent will describe the purpose of the study, the procedures to be followed, the risks and benefits of participation, all risks of the investigational agent(s) and/or study participation as listed in the model informed consent form, and all other elements of informed consent as required by regulation. A copy of the consent form will be given to the subject to keep.

In addition, any institution(s) conducting research according to the guidelines of this protocol is required to adhere to local and national laws and regulations governing the confidentiality and disclosure of health information.

### **11.2 Changes to the Protocol**

Any change or addition to this protocol requires a written protocol amendment that must be approved by CTEP and the Investigator before implementation. All amendments require approval by the IRB/IEC/REB of the treating institution. A copy of the written approval of the IRB/IEC/REB must be sent to the ODMC.

### **11.3 Subject Confidentiality**

In order to maintain subject privacy, all data capture records, drug accountability records, subject number. The Investigator will grant monitor(s) and auditor(s) from the AMC or the NCI and regulatory authorities (FDA) access to the subject's original medical records for verification of data gathered on the data capture records and to audit the data collection process. The subject's confidentiality will be maintained and will not be made publicly available to the extent permitted by the applicable laws and regulations.

## 11.4 Women and Minorities

This study is being conducted by the NCI-sponsored AIDS Malignancy Consortium (AMC). As part of their contractual obligations, each participating site within the AMC and the AMC as a whole is required to assure that the participation of women and minority subjects reflects the percentage representation of these populations in their geographic region and, for the AMC, the United States as a whole. As such, it is expected that the representation of subjects on this trial will reflect the constitution of the respective populations.

**Table 11-A: Accrual targets**

Racial Categories	Ethnic Categories				Total
	Not Hispanic or Latino		Hispanic or Latino		
	Female	Male	Female	Male	
American Indian/ Alaska Native	0	1	0	0	1
Asian	0	1	0	0	1
Native Hawaiian or Other Pacific Islander	0	1	0	0	1
Black or African American	3	17	1	4	25
White	5	57	3	17	82
More Than One Race	0	5	0	3	8
Total	8	82	4	24	118

## APPENDIX I: PERFORMANCE STATUS SCALES

Karnofsky Performance Scale		ECOG Performance Status Scale	
Percent	Description	Grade	Description
100	Normal, no complaints, no evidence of disease.	0	Normal activity. Fully active, able to carry on all pre-disease performance without restriction.
90	Able to carry on normal activity; minor signs or symptoms of disease.		
80	Normal activity with effort; some signs or symptoms of disease.	1	Symptoms, but ambulatory. Restricted in physically strenuous activity, but ambulatory and able to carry out work of a light or sedentary nature (e.g., light housework, office work).
70	Cares for self, unable to carry on normal activity or to do active work.		
60	Requires occasional assistance, but is able to care for most of his/her needs.	2	In bed <50% of the time. Ambulatory and capable of all self-care, but unable to carry out any work activities. Up and about more than 50% of waking hours.
50	Requires considerable assistance and frequent medical care.		
40	Disabled, requires special care and assistance.	3	In bed >50% of the time. Capable of only limited self-care, confined to bed or chair more than 50% of waking hours.
30	Severely disabled, hospitalization indicated. Death not imminent.		
20	Very sick, hospitalization indicated. Death not imminent.	4	100% bedridden. Completely disabled. Cannot carry on any self-care. Totally confined to bed or chair.
10	Moribund, fatal processes progressing rapidly.		
0	Dead.	5	Dead.

## APPENDIX II: SCHEDULE OF EVALUATIONS

Shaded visits should only be performed for those receiving study-provided topical treatments.

EVALUATIONS	Screening Visit -1	Visit 1 Week 0	Visit 2 Week 2	Visit 3 Week 8	Visit 4 Week 16	Visit 5 Week 20	Visit 6 Week 24	Visit 7 Week 26	Visit 8 Week 32	Visit 9 Week 40	Visit 10 Week 44	Premature d/c
Informed Consent	X											
HIV Documentation	X											
Complete Medical History	X											
Clinical Assessment 	X	X	X	X	X	X	X	X	X	X	X	X
Dispense Drug and Treatment Diary		X	X	X 			X 	X	X 			
Collect Diary / Adherence Assessment			X	X	X			X	X	X		X
Safety Bloodwork (CBC w diff, platelets)	X 											
CD4/CD8 (Counts + %)	X											
HIV-1 Plasma RNA	X											
Pregnancy Test	X	X	X	X	X	X	X	X	X	X	X	
Anal Biopsies	X			X 	X 	X			X 	X 	X	X
Anal Cytology	X					X					X	X
Anal Swab for HPV testing	X 			X	X	X			X	X	X	X
HRA	X	X		X 		X			X 		X	X
Optional anoscopy or HRA 			X 		X 			X 		X 		
Photo Documentation of Lesions		X		X	X	X	X		X	X	X	X
Smoking and Recent Sexual History Questionnaire		X				X					X	X
ACSR Donation	X 						X 					
Randomization		X					X 					

 At subsequent visits, routine laboratory testing and/or referral for testing for sexually transmitted infections should be conducted only if clinically indicated.

 See description in [Appendix IV](#) for modification to standard HRA procedure and criteria for biopsies at this visit with respect to the use of acetic acid. These HRA procedure modifications are for participants receiving study treatment only.

 Whole blood specimens to be collected at Visit -1 and Visit 6 (Week 24) for participants randomized at this visit, with participant consent for the ACSR donation.

 Cream will be weighed for adherence assessment and returned to the participant at Visits 3 and 8.

 Anal biopsies should only be performed at visits 3, 4, 8, and 9 if clinician notes any markers indicative of progression as listed in [Section 6.4.1](#).

 If the anal swab for HPV testing is not collected at the screening visit, it can be collected at entry (Visit 1) prior to HRA.

 As defined per [Section 6](#) for each visit.

 If participant can tolerate.

 Participants originally randomized to observation with HSIL at Week 20 may receive 5FU beginning at Week 24.

### **APPENDIX III: ANAL CYTOLOGY AND HPV SAMPLING**

**All anal cytology specimens will be examined at the local institution.**

The participant should undress so that buttocks are exposed, and either bend over the exam table or lay on their side in left lateral decubitus. The examiner should use one hand to spread the buttocks and expose the anal verge.

*Procedure for obtaining an anal swab specimen:*

A synthetic swab moistened in tap water will then be inserted as far as is comfortable into the anus, a minimum of 1-2 inches. If there is difficulty inserting the swab, the participant should also retract their buttocks and the swab reoriented in the canal. With pressure on the distal end of the swab rotate it firmly in a circular fashion for approximately 20 seconds and slowly remove from the canal. Do not retract the buttocks when the swab is close to the verge to ensure that it is sampled as well. Immediately immerse the swab in a liquid-cytology vial agitating vigorously over 20 to 45 seconds to disperse the cells.

For anal HPV testing: A second swab should be obtained and placed in Digene STM.

Specimen packaging and shipment instructions are provided in the Manual of Procedures (MOP). Specimens will be sent to the AMC Biorepository for storage before batch shipment to the AMC HPV Genotyping Core Laboratory.

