## **2.0 OBJECTIVES**

### **2.1 Primary Objective**

Complete response is defined as no anal biopsies with HSIL and cytology without HSIL at Week 20.

- To assess the efficacy of intra-anal topical 5FU for treatment of anal HSIL compared to observation only.

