### 6.6.1 The following evaluations will be performed, and laboratory samples will be collected for all participants.

- Clinical assessment: The participant's medical history will be updated for any changes. A review of systems for any new or changed local symptoms, such as hematochezia, dyschezia, erythema, swelling, or pruritus. A targeted physical exam should be performed as indicated (see [Section 6.2.1](#)).
- Pregnancy test: Urine or serum beta-HCG will be performed (and results obtained) when indicated (women of childbearing potential).
- Anal cytology (standard of care). If the result is not evaluable, then the site should repeat the cytology to obtain an interpretable result.
- Anal swab for HPV testing.

- HRA exam of the anal canal will be performed per [Section 9.1](#). The number of involved octants, location, and percent circumference of HSIL will be documented.
- All participants should have biopsies obtained as per [Appendix V](#). Please note that pathologists should remain blinded to the treatment assignment.
- If anal HSIL is present, then participants originally randomized to observation have the option of receiving 5-fluorouracil 5%. Cross-over should occur as outlined in [Section 3.4.3](#). If these participants decline cross-over, then they should be referred off study to be treated according to the local standard of care as described below.
- Participants originally randomized to 5-fluorouracil 5% arms, with HSIL at Week 20 should be referred off study to be treated according to the local standard of care. Participants can be treated with ablative methods such as office-based infrared coagulation, hyfrecation, electrocautery, laser, or 80-85% trichloroacetic acid if preferred. Topical treatments such as 5-fluorouracil 5%, imiquimod, Veregen 15%, or cidofovir should not be used.
- Condyloma can be treated at the discretion of the local provider with ablative methods such as office-based infrared coagulation, hyfrecation, electrocautery, laser, or 80-85% trichloroacetic acid if preferred. Topical treatments such as 5-fluorouracil 5%, imiquimod, Veregen 15%, or cidofovir should not be used.
- All lesions, all aspects of the anal transformation zone, distal canal and perianus will be photographically documented.
- AMC-088 Smoking Status and Recent Sexual History Questionnaire: A review of smoking and recent sexual behavior.

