### **9.1    Definition of Clinical Response (by Subject)**

- 9.1.1    Complete Response (CR): The absence of HSIL histology for all biopsies and the absence of HSIL cytology.
- 9.1.2    Partial Response (PR): 1) The regression of HSIL histology but HSIL cytology is present, or 2) Reduction in number of octants with HSIL.
- 9.1.3    No Response: The presence of HSIL histology with no change in the number of octants with HSIL with or without HSIL cytology.
- 9.1.4    Spontaneous Regression: The absence of HSIL histology and HSIL cytology following no treatment.

Please note that LSIL is treated the same as no SILs for the purpose of these definitions. For example, a participant with all biopsies showing LSIL and cytology showing LSIL would be considered a CR.

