### 10.7 Primary Analyses

The primary analysis population for efficacy and safety is an intent-to-treat (ITT) population, which consists of all participants who are randomized to 5-fluorouracil 5% or observation. The proportion of participants achieving complete response in the 5-fluorouracil 5%, and the proportion of participants with spontaneous regression in the observation arm will be calculated as the number achieving complete response or experiencing spontaneous regression through the primary endpoint visit (Week 20) divided by the number in the intent-to-treat population. For the treatment comparison (topical 5-

fluorouracil 5% vs. observation) the proportions will be compared across sites using stratified Mantel-Haenszel-Cochran tests at the one-sided 0.05 alpha level. This means that participants who drop out or do not provide evaluable data contribute to the analysis since they are included in the denominator, i.e., they are essentially treated as failures.

Since the imiquimod arm was stopped early, we will describe comparisons between imiquimod and observation using only the participants randomized to imiquimod and observation prior to closure of the imiquimod arm. As a secondary objective, imiquimod 2.5% and topical 5-fluorouracil 5% will be compared using a stratified Mantel-Haenszel-Cochran test at the two-sided 0.05 alpha level using participants randomized prior to the closure of the imiquimod arm.

The primary endpoint will include intra-anal HSIL present on cytology or histology. Perianal HSIL will be descriptively reported separately, as well as combined with the primary endpoint. In addition to the primary intent-to-treat analysis (which includes all randomized participants), we will perform a sensitivity analysis that treats participants who receive HSIL treatment other than randomized treatment (or observation participants that receive any treatment) prior to Week 20 as failures; participants who are lost to follow-up or inevaluable are also still treated as failures. We will also perform a per-protocol analysis using the subset of participants who were adherent to the protocol.

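### HSIL on Week 20 cytology alone makes a primary-endpoint failure, but blinding, central review and adjudication are specified only for biopsies

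*Combined protocol and SAP*

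**What the plan says.** Section 2.1 sets the primary endpoint: "Complete response is defined as no anal biopsies with HSIL and cytology without HSIL at Week 20". Section 9.1.1 repeats it as "The absence of HSIL histology for all biopsies and the absence of HSIL cytology". Section 9.1.2 classes "The regression of HSIL histology but HSIL cytology is present" as a partial response, and 10.7 confirms that "The primary endpoint will include intra-anal HSIL present on cytology or histology".

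The safeguards for the two components differ.

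- **Biopsies.** Section 6.6.1 says "Please note that pathologists should remain blinded to the treatment assignment". The sentence recurs in 6.11.1 and 6.12, each time in the bullet on biopsies. Section 10.9.2 adds "Slides from all biopsies used for eligibility and slides from all biopsies obtained post-randomization will be submitted for central review" by one pathologist, with disagreements over the AIN category sent for adjudication. Appendix VII describes the material sent: one H&E slide per biopsy.
- **Cytology.** It has its own bullet, labelled standard of care, with no blinding sentence. Appendix III says "All anal cytology specimens will be examined at the local institution". The one quality provision at Week 20, in 6.6.1, is "If the result is not evaluable, then the site should repeat the cytology to obtain an interpretable result".

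The Synopsis describes the trial as open-label.

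**The concern.** The plan treats a masked, centrally reviewed and adjudicated reading as necessary for histology. It gives no reason for leaving out the other component, which can decide the outcome by itself. Site staff who collect and submit the cytology know the arm, and nothing in the plan keeps that knowledge from the cytology reader.

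A reader who knows that a participant has just finished 5FU could discount atypia as a treatment effect, or could over-call it. The first would raise the 5FU response rate and separate the arms; the second would lower it and bring them together. In either case the primary result would partly reflect how cytology was read, and no prespecified binary result on the reviewed component would stand beside it.

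**Working it through.** **1. When cytology decides the outcome (9.1, 10.7)**

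| Biopsies | Cytology | Primary endpoint |
|---|---|---|
| all clear | no HSIL | response |
| all clear | HSIL | failure (classed as PR) |
| any HSIL | either | failure |

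Cytology can remove a response when all biopsies are clear. It cannot create one against HSIL histology.

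**2. How many participants.** Section 10.3 gives 40% vs 10%, and 10.1 gives 35 per arm.

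- 5FU: 0.40 × 35 = 14. Observation: 0.10 × 35 = 3.5.
- If the design rates are response rates, these are minimum counts of participants with clear biopsies, because cytology-only failures would add to them.
- One reclassification: 1/35 = 2.9 percentage points.

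**3. Effect of single calls.** The unstratified Mantel-Haenszel statistic, as an approximation to the site-stratified test, is Z = (a − m/2)/√V, with V = 35 × 35 × m(70 − m)/(70² × 69). Here a is the number of 5FU responses and m the total responses. The final bound in Table 10-A is 1.955.

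| 5FU vs observation | m | √V | Z |
|---|---|---|---|
| 14 vs 4 | 18 | 1.842 | 5/1.842 = 2.72 |
| 13 vs 5 | 18 | 1.842 | 4/1.842 = 2.17 |
| 12 vs 3 | 15 | 1.729 | 4.5/1.729 = 2.60 |
| 11 vs 4 | 15 | 1.729 | 3.5/1.729 = 2.02 |
| 10 vs 4 | 14 | 1.685 | 3/1.685 = 1.78 |
| 10 vs 5 | 15 | 1.729 | 2.5/1.729 = 1.45 |

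One call in each arm moves 14 vs 4 to 13 vs 5, or 12 vs 3 to 11 vs 4, and both results stay above the bound. From 11 vs 4, one more lost 5FU response (10 vs 4) falls below it.

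**4. Possible bias, under assumed rates.** The baseline comes first. Table 10-A states β = 0.100. With 35 per arm and one-sided 0.025, power = Φ[(0.3√35 − 1.96√(2 × 0.25 × 0.75))/√(0.24 + 0.09)] = Φ(1.00) = 84.1%, or 85.2% by exact enumeration at 1.955. The stated 90% is not reproduced at that alpha. That is a separate matter, and 85% is the reference here.

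The documents give no rate of HSIL cytology among participants with clear biopsies. I assumed 10%, 20% and 30%, took the assumed clearance as histologic clearance, and used the exact single-look test at 1.955.

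| Extra HSIL calls | 10% | 20% | 30% |
|---|---|---|---|
| Both arms, 40% vs 10%: power | 80% | 74% | 67% |
| 5FU only, 40% vs 10%: power | 76% | 63% | 49% |
| Observation only, 40% vs 10%: power | 88% | 91% | 94% |
| Observation only, no effect, clearance 10%: type I error | 3.9% | 5.2% | 7.0% |
| Observation only, no effect, clearance 40%: type I error | 5.3% | 10.5% | 18.8% |

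For comparison, extra calls of 10% in both arms with no effect give type I error of 2.8% at 10% clearance and 2.6% at 40%. The inflation therefore comes mainly from the difference between arms.

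**5. Planned analyses that might already answer the question**

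- 10.7: perianal HSIL reported separately and combined; off-protocol treatment counted as failure; per-protocol. Each keeps cytology in the definition.
- 10.8, quadrants with HSIL on biopsy: histology only, but ordinal, with no stated rule for missing results.
- 10.8, CR or PR: counts cytology-only failures as responders, but also counts any reduction in octants.

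None gives the binary response comparison on histology alone.

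**The case against.** A reader might infer that the cytology readers are unmasked. The documents do not say so. The blinding sentence names pathologists and no specimen type, and Appendix VII has a designated on-site pathologist review all pathology specimens, so the sponsor could say that it already covers cytology. An open-label design does not show that laboratory readers know the arm. No section describes what accompanies a cytology specimen, and the Manual of Procedures, cited in Appendix III for packaging and shipment, is not available here. This objection stands: the supportable statement is that no masking is specified for cytology.

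A reader might also infer that no analysis is free of cytology. The quadrant comparison in 10.8 is, and zero quadrants is histologic clearance. What remains is the missing binary analysis.

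Calling cytology half of the endpoint would overstate its reach, since it acts only where biopsies are clear. At the design rates, over-calling in the observation arm can act on only about 3.5 participants. The largest inflation above (18.8%) needs 40% clearance without any treatment effect, against the plan's assumed maximum of 10% regression under observation.

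**Conclusion.** The gap is real and moderate in importance. One component of the primary endpoint can by itself turn a histologic clearance into a failure, and the plan states none of the masking, central review or adjudication for it that it states for the other. It concerns about 14 vs 3.5 participants at the design rates, each worth 2.9 points.

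The documents do not support saying that bias is present, that it would favour 5FU, or that one call in each arm would overturn the result: from 12 vs 3, Z falls from 2.60 to 2.02, still above 1.955. The power and type I error figures illustrate assumed rates of 10% to 30% and an unstratified single-look test; they do not estimate this trial. Section 10.7 states one-sided 0.05 where 10.6.2 states 0.025. At the 0.05 level (cutoff 1.645), 10 vs 4 would still pass and 10 vs 5 would not. The conclusion does not depend on which level applies.

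**What to change.** 1. In 6.6.1, 6.11.1 and 6.12, extend the blinding sentence explicitly to cytology readers, and state that no arm or study-treatment information goes with the specimen. Apply this to all reads still to come.
2. In 10.7, add a sensitivity analysis of complete response defined on centrally reviewed and adjudicated intra-anal histology alone, using the same stratified test and the same rule that missing or inevaluable participants are failures. Report by arm the number of failures caused by cytology only.

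The cost is one sentence on specimen submission and one extra table from data already being collected. The primary endpoint does not change.

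The limit is timing. Enrollment closed on 01 July 2023 and this version is dated 02 August 2023. Week 20 is 140 days after randomization, so on that date only participants randomized after about 15 March 2023 still had a nominal Week 20 visit ahead. That is 108 days of accrual at roughly one participant per month (10.1), or about four participants. Cytology already read cannot be re-masked, so only the histology analysis covers those participants.
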